*Primary objective(s):* To determine the feasibility of performing HIVM in patients with deep space solid tumors during standard course of surgical resection. A successful intravital microscopic observation will include the ability to complete each of the following:

1. Identify and measure vessels associated with tumor
2. Determine vessel density per 10x field
3. Visualize vital dyes within the vessels (fluorescein)
4. Calculate the blood flow velocity of the vessels and tissue penetration of fluorescein as a marker of vessel permeability.
5. Obtain these vessel parameters after administration of an IV fluid bolus and/or vasopressor administration (phenylephrine or vasopressin) during the normal course of the surgical resection.

*Secondary objective(s):*

1. Compare the microscopic observation of the tumor-associated vessels with normal tissue (e.g. peritoneal surface) in each individual subject.
2. Correlate the microscopic observations of the tumor-associated vessels with pathologic grade of tumor.
3. To correlate the microscopic observation of the microvasculature with tumor-specific and overall survival.

Study Design: This is a non-randomized, single center, study of HIVM observation in subjects with deep space solid tumors undergoing surgical resection.

All subjects will meet the inclusion and exclusion criteria prior to participation in this study. Standard evaluation by the Preoperative Anesthesia clinic at Mayo Clinic Florida may include additional testing such as EKG, chest x-ray, and/or pulmonary function tests.

The study will be performed in two parts. Part 1 will enroll 10 patients with an expected feasibility rate of 70%. Whereas the feasibility rate in primary melanoma was 90%, the expected feasibility rate for deep space tumors may be lower as the site is in an anatomically deeper location. If Part 1 is not met (i.e. in three or more patients), the primary objective would not be considered technically feasible, and then the study will be stopped. If Part 1 is fulfilled, then the study will continue with an additional 40 patients enrolled (total of 50 patients). Accrual is expected to take 2.5 years.

*Inclusion criteria:*

1. Age  $\geq$  18 years of age.
2. ECOG Performance Status of  $\leq 2$ .
3. Measurable tumor by direct visualization requiring surgical resection in the OR.

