Technical difficulties with the microscope apparatus (e.g. malfunction of the software or structural damage to any of the microscope components) or unforeseen events during the course of surgery that are unrelated to the study intervention but that result in the termination of the surgery (e.g. adverse reaction to anesthetic prior to administration of fluorescein or hemodynamic instability from a complication of the surgery) will not be considered failures of the primary objective. In these circumstances, the subject will be considered to be off-study and be replaced with a subsequent patient. If vasopressors are not administered during the course of the surgery, the patient data will still be included in the study as it addresses Aim 1.

Off-line analysis of digitally recorded live video will be performed using parameters and statistical methods that have been developed in our preclinical imaging studies.[1] Lumenal cross-sectional diameter (D) of vessels and velocity (V) of dye labeled cells will be measured in off-line observations. Wall shear rate ( $\gamma$ ) will be calculated as  $8(V \div D)$ .[44] Vessel density will be determined by measuring the calculated blood vessel area as a percent of the total visual field area. If visible, the uptake of fluorescein will be measured as a diffusion rate (distance from tumor vessel over time) and as a percent of the total tumor field observed (percent of visual field expressed as surface area with dye detected). Blood flow velocity will be determined by the equation  $Q = (RBC \text{ velocity}/1.6) \times (d/2) \times \pi$ . Software is available from Mauna Kea, which can analyze and calculate these data.

These data will be calculated and recorded in a spread sheet that will also be saved onto a password-protected hard drive in the Principal Investigator's laboratory. Additionally, all data will be de-identified and provided to the Biostatistician. Generated data and the raw video images will be stored for review at any time to satisfy any audit of the collected data. This saved data will readily allow the determination of a successful observation including the identification of tumor vessels, the associated vessel measurements, vessel density, and dye enhanced imaging acquisition.

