## **9 STATISTICAL METHODOLOGY**

Initially ten patients will be treated to determine the feasibility of HIVM for deep space tumors. This first part of the study is a pilot study of feasibility. If seven or more patients are deemed a success by meeting all of the criteria below, then HIVM will be deemed feasible in the study of deep space tumors. Criteria include the ability to complete each of the following:

1. Identify and measure vessels associated with tumor
2. Determine vessel density per 10x field
3. Visualize vital dyes within the vessels (fluorescein)
4. Calculate the blood flow velocity of the vessels and tissue penetration of fluorescein as a marker of vessel permeability.

If the true success rate is 60%, the probability of deeming HIVM feasible is 63%; if the true success rate is 70%, then the probability of deeming HIVM feasible is 88%; and if the true success rate is 90%, then the probability of deeming HIVM feasible increases to 99%.

If HIVM is deemed feasible, then an additional 40 patients will be accrued to this study in order to address the following:

1. Post-operative comparison of the microvasculature of tumor with normal tissue (peritoneum) in each individual subject using vessel diameters, vessel density, detection of intravital dye and flow rates.
2. Post-operative correlation of the microvasculature with pathologic features of the tumor (i.e. tumor grade) at the time of the final pathology report (5-7 days after surgery).
3. Post-operative correlation of the microscopic observation of the tumor microvasculature tumor-specific and overall survival.

An abnormal HIVM observation is defined by any of the following criteria:

1. Aberrant vessel structure compared to normal tissue, which includes tortuosity of the vessel wall or a closed loop formation.
2. Aberrant vessel branching patterns compared to normal tissue, which includes erratic and disorganized branching points.
3. Blood vessel density that is less than or greater than one standard deviation of the blood vessel density observed in normal tissue.
4. Inability to detect flow or fluorescein within a vessel.
5. Average blood flow rate through observed vessel that is less than one standard deviation of the average blood flow rate through a normal vessel.

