A matched analysis will be performed for observations of microvasculature between the tumor and normal tissue. For dichotomous variable comparisons between vessel structure (normal vs aberrant), vessel branching patterns (normal vs aberrant), or detection of intravital dye (present vs absent), a McNemar's test will be performed. For continuous variable comparisons between blood vessel density and average blood flow rate, a paired t test will be performed.

Associations between characteristics for the baseline (normal peritoneal microvasculature observed surrounding the tumor) and tumor itself will be depicted with graphics, correlations, and model results.

Similar analyses will be performed to compare baseline observations with those performed after fluid bolus and/or vasopressor administration.

Adverse event and complication rates will be described using upper one-sided 95% Clopper Pearson confidence limits.

Overall survival will be defined as the duration of time from diagnosis to time of death. Disease specific survival will be defined as the time from surgery to death due to recurrence. Overall survival and disease specific survival will be generated using standard Kaplan-Meier methodology.

A maximum of 50 subjects will be enrolled in this study (initially 10 to determine feasibility and then 40 additional subjects if deemed feasible). The accrual rate is estimated at 1-2 subjects per month, and the estimated study duration is 30 months (2.5 years).

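### Section 9 scores undetected dye or flow as a vessel finding in two places, without separating a non-perfused vessel from one that could not be read

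*Combined protocol and SAP*

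**What the plan says.** **Feasibility.** Under sections 3.3 and 9 a patient succeeds only if all four items are met. In section 9, item 3 is "Visualize vital dyes within the vessels (fluorescein") and item 4 includes a calculated flow velocity. The Part I rule is "If seven or more patients are deemed a success by meeting all of the criteria below, then HIVM will be deemed feasible". The Synopsis (Study Design) says "Part 1 will enroll 10 patients with an expected feasibility rate of 70"%, and adds "Whereas the feasibility rate in primary melanoma was 90%, the expected feasibility rate for deep space tumors may be lower" because the site is deeper.

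**Replacement.** Section 4.2 says that microscope malfunction, and surgery ended for reasons unrelated to the study intervention, "will not be considered failures of the primary objective". Those patients go off study and are replaced. No other failed observation is replaced.

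**Scoring in the secondary analyses.** Section 9 calls an observation abnormal if any one of five criteria is met. Criterion 4 is "Inability to detect flow or fluorescein within a vessel". Dye detection, present or absent, is compared between tumor and normal tissue by McNemar's test; density and average flow rate are compared by paired t test. The comparison before and after fluid or vasopressor is to use similar methods.

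**What is not given.** Section 9 has no 'not evaluable' category, no analysis set for each secondary endpoint, and no rule for unreadable parameters in the grade, survival or paired t analyses. It does not say which analysis uses the abnormal classification.

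**The concern.** One event has two meanings. If dye or flow cannot be seen in a vessel, the patient fails feasibility item 3 or 4, which is a statement about the measurement. Criterion 4 and the absent code then treat that event as a statement about the vessel. A non-perfused tumor vessel is a legitimate abnormal finding, but the text gives the reader of the video no way to record it separately from poor access, motion or depth.

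The Synopsis itself expects lower feasibility because of anatomical depth, so failures unrelated to vessel biology are foreseen. If they occur mainly in tumor tissue, the tumor-normal dye comparison is pushed towards a difference. If the abnormal classification is later related to grade or survival, unreadable images become part of the exposure. The association is diluted when failure is unrelated to outcome, and can be created when failure tracks less accessible tumors with worse outcome. Aim 1 proposes HIVM as a predictive biomarker, so what the word abnormal means decides whether such a result can be interpreted.

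**Working it through.** **1. The plan's own figures.** Section 9 gives 63%, 88% and 99% as the probability of deeming HIVM feasible at true success rates of 60%, 70% and 90%. The exact binomial probability of at least 7 successes in 10 is 38.2%, 65.0% and 98.7%. Only the last agrees. This is a separate error; the counts below use the success rates, not these probabilities.

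**2. How many failures remain.** Inputs: 50 patients in all (section 9); 40 in Part II, under which section 3.2 places the secondary objectives; success rates of 70% and 90% (Synopsis) and 60% (a section 9 scenario). Expected failures = N × (1 − success rate), with 95% binomial ranges:

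| Success rate | Of 50 | Of 40 |
|---|---|---|
| 90% (melanoma) | 50 × 0.10 = 5 (1–9) | 40 × 0.10 = 4 (1–8) |
| 70% (expected here) | 50 × 0.30 = 15 (9–22) | 40 × 0.30 = 12 (7–18) |
| 60% (scenario) | 50 × 0.40 = 20 (13–27) | 40 × 0.40 = 16 (10–22) |

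Part II opens only after at most 3 failures in 10. Given that, expected failures in the first 10 are 0.96, 2.14 and 2.43, so the totals of 50 become 0.96 + 4 = 5.0, 2.14 + 12 = 14.1 and 2.43 + 16 = 18.4. The change is small.

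**3. How many of these are scored as findings.** Criterion 4 applies within a vessel, so a vessel must have been identified. A patient with no identifiable vessel, no readable density, or only a missing tissue-penetration measure does not meet it. The documents give no split, so the counts in step 2 are ceilings for criterion 4 at each rate.

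**4. Effect on the dye comparison.** Suppose d patients have dye unread in tumor but seen in normal tissue, with no pair the other way. The exact two-sided McNemar p is 2 × 0.5^d:
- d = 5: 0.0625
- d = 6: 0.031
- d = 15: 0.00006

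Six one-sided imaging failures are therefore enough for nominal significance with no biological difference.

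**5. Effect on a grade comparison, if it used the abnormal classification.** Let a be the true proportion abnormal and f the proportion of failures, all coded abnormal. The observed proportion is (1 − f)a + f. The proportions below are assumed.
- True 40% versus 70%, f = 0.30 in both grades: 0.7 × 0.4 + 0.3 = 58% and 0.7 × 0.7 + 0.3 = 79%. The 30-point difference becomes 21. At f = 0.10 it is 46% versus 73%, or 27 points.
- No true difference (50% each), f = 0.10 versus 0.30: 0.9 × 0.5 + 0.1 = 55% and 0.7 × 0.5 + 0.3 = 65%. A false 10-point difference appears.

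**6. Upper-bound illustration for survival.** This is a simulated Cox model with 50 patients, 50% truly abnormal, true hazard ratio 2.5, baseline hazard 0.10 per year and 5 to 7.5 years of follow-up. All of these inputs are assumed, and every failure is coded abnormal.
- 30% failures: median hazard ratio 2.03 and power 39%, against 2.52 and 52% with failures set aside.
- 10% failures: 2.30 and 58%, against 2.50 and 64%.
- No true effect, failed patients at twice the hazard: spurious hazard ratio 1.39 (30% failures) or 1.16 (10%).

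If only half of the failures reach criterion 4 and the rest are classed by their true status, the 30% case gives 2.25 and 53%, against 2.51 and 52% with all failures set aside. The power loss disappears, and the spurious ratio falls to about 1.17.

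**The case against.** Several parts of the defence stand.

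- **Criterion 4 presupposes a vessel.** A reader might infer that every failed observation is entered as abnormal. The wording does not support that: a field with no identified vessel does not meet the criterion.
- **Absent flow can be real.** Section 1 describes abnormal flow as a feature of tumor vessels. Scoring non-perfusion as abnormal is reasonable; the fault is that it cannot be told apart from a failed read.
- **Criterion 4 is not the only rule.** The McNemar comparison also gives undetected dye a code. This answers a claim that no rule exists, but that code has the same ambiguity.
- **The exposure is not stated.** A reader might infer that the abnormal classification is what will be related to grade and survival. Section 9 does not say so, and for survival it names only Kaplan-Meier methods.
- **No paired sample size is claimed.** A reader might infer that the paired tests fall short of a planned 50 pairs. The plan states neither 50 pairs nor a detectable effect, and section 3.2 ties the secondary aims to 40 patients. A patient missing only one parameter still contributes pairs for the others.
- **The survival figures depend on the inputs.** The study collects data for up to 10 years, longer than simulated. If 80% of tumors were truly abnormal, power at 30% failures would be 21% with failures coded abnormal and 23% with them set aside.

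These points limit the size of the problem and its reach into grade and survival. They do not remove the double meaning in criterion 4 and the absent dye code.

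**Conclusion.** The point holds for the two scoring rules. As written, criterion 4 and the McNemar dye comparison can record an imaging failure as vessel biology. Failures not covered by replacement are expected in about 15 of 50 patients (12 of 40) at the planned 70%, and 5 of 50 (4 of 40) at the melanoma rate. An unknown part of these reaches criterion 4.

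The firmest consequence is for the dye comparison, where six failures confined to tumor give p = 0.031. That figure assumes no opposite discordant pairs. Contamination of the grade and survival results is conditional on their using the abnormal classification, and the hazard ratios above are an upper-bound illustration, not a forecast. The change should be made, because it determines what a positive secondary finding would mean. It does not affect the primary feasibility decision.

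**What to change.** In section 9:

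1. Limit criterion 4 and the absent dye code to an identified vessel in an adequate image in which dye or flow is seen elsewhere in the same field or tissue.
2. Code every other unreadable parameter 'not evaluable'.
3. Analyse each secondary endpoint in patients evaluable for that parameter. State whether the base is the 40 Part II patients or all 50, and which analyses use the abnormal classification.
4. Report not-evaluable patients by grade and survival.
5. Use 'not evaluable' coded as abnormal or absent only as a sensitivity analysis.

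The cost is wording in section 9 and one extra code on the video read form. Reads are made off-line from stored video, so no new procedure is needed, but the rule should be fixed before outcomes are known. Each secondary analysis will have fewer patients. If every failure made every parameter unreadable, 35 to 45 of 50 (28 to 36 of 40) would remain at 70% to 90% feasibility; the number for a single parameter should be higher. A tumor with no perfusion anywhere would also be coded 'not evaluable', which is a further reason to keep the sensitivity analysis.

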1-2 mL of 10 or 25% fluorescein will be injected intravenously and observation will continue until loss of fluorescence over 2-4 areas of both grossly normal and tumor tissue. IVM is continuously performed at the time the fluorescent agent is injected and video is recorded in real-time. The fluorescein is almost immediately visible within the microscopic field, and the vessels are quickly outlined in great detail. The fluorescence lasts for a few minutes (2-3 minutes) and then either fades or begins to permeate through the tissue. The extravasation of dye will be determined by visualizing fluorescence outside of the defined vessels for a total time of 5 minutes. The distance from the vessels will be measured, recorded, and expressed as a function of time (extravasation rate) in an analysis performed off-line from the digitally recorded video. On average, the total observation time per field is 1-2 minutes.

During the course of the surgery, if fluid boluses and/or vasopressors (e.g. vasopressin and/or phenylephrine) are required and administered to maintain blood pressure during the resection, another round of IVM observations will be performed with a second dose of 1-2 mL of fluorescein. Communication with anesthesia will indicate when fluid boluses and/or vasopressors are administered, in order to coordinate the observation.

At the completion of the entire observation period, the microscope will be removed and sterilized between uses. This would complete the observation period, which is anticipated to take 10 – 12 minutes total time. The observation will take place during the course of standard surgery and is not anticipated to delay or lengthen the duration of the procedure. In fact, during this observation period, other portions of the surgical procedure will be performed, including pathologic biopsy assessment, margin assessment, intra-abdominal irrigation, drain placement and securement, implantation of hemostatic agents (Surgicel, Tissell spray, GelFoam, etc), or in the case of more than one tumor or satellite tumors, additional dissection of the remaining tumors. The patient will recover in the PACU per standard protocol. The patient will be monitored for any allergic reactions and/or side effects to fluorescein administration and treated appropriately as described in previous sections.

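### The plan does not say how vessels without detectable flow enter average flow, or that the second round images the same areas; if they are omitted, closure of slow vessels can look like enhanced flow

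*Combined protocol and SAP*

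**What the plan says.** Section 4.2 obtains velocity from moving, dye-labeled cells on recorded video: "Lumenal cross-sectional diameter (D) of vessels and velocity (V) of dye labeled cells will be measured in off-line observations". "Blood flow velocity will be determined by the equation" then introduces a formula whose inputs are red-cell velocity and vessel diameter. The same section explains that fluorescein outlines the vessels and that fluorescence lasts two to three minutes before it fades or passes into the tissue.

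In the first round, "observation will continue until loss of fluorescence over 2-4 areas of both grossly normal and tumor tissue". If a bolus or vasopressor is given, "another round of IVM observations will be performed with a second dose of 1-2 mL of fluorescein". Nothing asks for the same areas or the same vessels.

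Section 9 lists undetectable flow ("Inability to detect flow or fluorescein within a vessel") and low average flow ("Average blood flow rate through observed vessel that is less than one standard deviation of the average blood flow rate through a normal vessel") as two separate criteria for an abnormal observation. On testing, it says: "For continuous variable comparisons between blood vessel density and average blood flow rate, a paired t test will be performed". The before/after comparison has one sentence: "Similar analyses will be performed to compare baseline observations with those performed after fluid bolus and/or vasopressor administration". Aim 2 in the Synopsis asks whether the enhanced tumor flow seen in the team's animal models can be reproduced in patients.

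**The concern.** The flow formula gives no value where no velocity is recorded, and the plan supplies no rule for that case. A vessel that closes before the second dye dose may not be outlined at all. Unless the reader has returned to the same field and knows the vessel was there, it leaves no entry in the data.

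The before and after averages may then cover different sets of vessels, with membership depending on the outcome, because a vessel counts only if it still flows. If the vessels that stop are mainly slow ones, the average over the rest goes up although no vessel has sped up. Aim 2 looks for an increase, so the error would run in favor of the hypothesis. A reported rise could be a fall in perfusion.

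**Working it through.** The documents give no standard deviation, effect size, power or significance level for the flow comparison, so there is no stated figure to reproduce. The check asks how far the two possible treatments of a closed vessel can differ. All vessel flows, coefficients of variation (CV), closing fractions and the two-sided 0.05 level below are assumptions.

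**1. Ten vessels.** Take flows of 100, 200, ..., 1000 (arbitrary units). Total 5500, mean 550. The two slowest close and the rest do not change; the remaining total is 5500 − 300 = 5200.
- Closed vessels dropped: 5200/8 = 650, and 650/550 − 1 = +18.2%.
- Closed vessels as zero: 5200/10 = 520, and 520/550 − 1 = −5.5%.
- The two are linked: perfused fraction × mean among flowing vessels = 0.8 × 650 = 520.

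If the eight open vessels also slow by 10%, the total is 4680. Dropping gives 585 (+6.4%); zero gives 468 (−14.9%). The average can rise while every vessel is slower or closed.

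**2. General form.** Let vessel flow be lognormal with log-SD σ = √ln(1 + CV²), and let the slowest fraction f close. The share of total flow they carried is S = Φ(z_f − σ).
- Change if dropped: (1 − S)/(1 − f) − 1.
- Change if zero: −S.

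Example, CV 0.5 and f = 0.2: σ = 0.472, z_f = −0.842, S = Φ(−1.314) = 0.094. Dropped: 0.906/0.8 − 1 = +13.2%. Zero: −9.4%.

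| CV | f | Dropped | As zero |
|---|---|---|---|
| 0.3 | 10% | +4.7% | −5.8% |
| 0.3 | 20% | +9.0% | −12.8% |
| 0.3 | 30% | +13.3% | −20.7% |
| 0.5 | 10% | +6.7% | −4.0% |
| 0.5 | 20% | +13.2% | −9.4% |
| 0.5 | 30% | +20.1% | −15.9% |
| 0.8 | 10% | +8.5% | −2.4% |
| 0.8 | 20% | +17.4% | −6.1% |
| 0.8 | 30% | +27.2% | −11.0% |

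The sign differs in every row. If closure were unrelated to speed, dropping would show no change on average, while flow per original vessel would fall by f.

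**3. Effect on the paired t test.** Simulation with 1,000 runs, 10 vessels per patient, CV 0.5, between-patient log-SD 0.3, and no vessel speeding up. The repeat measurement on the same fields has log-SD 0.1. With 40 patients and 20% closing:
- same fields, closed vessels dropped: significant increase in 100% of runs;
- different fields, closed vessels dropped: significant increase in 86%;
- same fields, closed vessels as zero: significant decrease in 100%.

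With only 10 patients contributing a second round, the different-fields figure is 26%. Every simulated patient loses the same fraction of vessels, so these rates show that the error is systematic; they do not forecast the trial.

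The upward bias comes from dropping closed vessels, not from changing fields: it is present on matched fields too. Unmatched fields add noise, and they prevent a closed vessel from being recognized as one.

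**4. Other planned analyses.** Dye detection is tested as present or absent. Read as one result per patient, it can hardly show partial closure: seeing dye in tumor vessels is a success criterion (Section 3.3), so a successful patient starts as present and changes only if dye is absent throughout round two. Vessel density, defined as vessel area over field area, could fall with closure. But it also moves with vessel diameter, may come from other fields, and is tested apart from flow.

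**The case against.** The strongest reply is that the plan never says no-flow vessels are excluded. A reader might infer such a rule from the velocity-based formula and the separate no-flow criterion, but the documents do not state it. The criterion speaks of an observed vessel, not a flowing one, and a visible vessel with static cells could be scored zero. Section 4.2 also refers to methods from the team's preclinical work, which may settle the point. This stands, and it is why the point is conditional.

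A reader might also infer that closure disappears from the results altogether. It does not. Undetectable flow makes an observation abnormal in its own right, and density and dye detection are compared as well. These safeguards are real but coarse, and neither corrects a flow result with the wrong sign.

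Third, the illustration assumes that slow vessels close. The documents do not say that they do, and the second round may follow a fluid bolus alone, for which no closing mechanism is offered. That limits how often the problem would arise, not whether the average can mislead when it does.

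Fourth, scoring every failed reading as zero would create the opposite bias. Dye fades within minutes, so a missing velocity need not mean absent flow. First-round areas may also have been dissected or removed by the second round. Both objections stand and shape the fix.

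Last, the Part I decision depends on whether the parameters can be obtained, not on mean flow. It is unaffected.

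**Conclusion.** The concern holds in conditional form. Two things are unspecified: how vessels without detectable flow enter the average, and whether round two returns to the same areas. If such vessels are omitted, which is the likely default because dye is what makes a vessel visible, selective closure of slow vessels turns a fall in flow per original vessel (about 2% to 21%) into an apparent rise (about 5% to 27%). The size rests on assumed lognormal flows, a CV of 0.3 to 0.8, closure of the slowest 10% to 30%, and no change in the other vessels. The sign reversal held across that whole range.

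The documents do not support saying that the plan discards these vessels by rule, that unmatched fields are themselves the source of the upward bias, or that no planned analysis could reveal closure. The point affects the interpretation of Aim 2. For tumor versus normal tissue, the same question about the flow average is open, but no size is claimed here.

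**What to change.** In Section 4.2, state that round two re-images the areas recorded in round one where they are still present and accessible, and that the record shows when they are not.

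In Section 9, for the before/after comparison:
- use the vessels identified in round one, in those areas, as the denominator;
- report the fraction of them that are perfused in each round, and test it as a paired outcome within patient;
- report mean flow in two ways: among flowing vessels, and with vessels that are adequately imaged but show no flow counted as zero;
- record vessels that cannot be read for technical reasons as missing, not zero, and give their number.

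The cost is marking fields at round one, some extra video coding, and some patients without matched fields, whose number should be reported. No extra procedure or staff is needed. The coding can be done later from stored video; field matching cannot be recovered after surgery, so the Section 4.2 change should be made first.
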